## Observational Study information

Acronym / Title	A Drug Utilization Study of Xofigo Use in Sweden
Protocol version identifier	Version 2.0
Date of last version of protocol	10- Oct-2014
IMPACT study number	17399
Study type	 non-PASS  PASS      Joint PASS:  YES  NO
EU PAS register number	TBC
Active substance	Radium-223 dichloride
Medicinal product	Xofigo®
Product reference	BAY88-8223
Procedure number	NA
Marketing authorization holder(s)	Bayer Pharma AG, Berlin, Germany
Research question and objectives	The aim of this study is to assess the use of Xofigo including patients with a diagnosis of castration-resistant prostate cancer with bone metastasis (mCRPC) and patients in whom Xofigo may be potentially used off-label.
Country(-ies) of study	Sweden
Author	[name], Department of Urology, Karolinska University Hospital, Stockholm, [contact]

## 2 List of abbreviations

AE	Adverse Event
ADR	Adverse Drug Reaction
AR	Adverse Reaction
CRF	Case Report Form
CRPC	Castration Resistant Prostate Cancer
DMP	Data Management Plan
EC	European Commission
EDC	Electronic Data Capture
EFPIA	European Federation of Pharmaceutical Industries and Associations
EMA	European Medicine Agency
ENCePP	European Network of Centers in Pharmacoepidemiology and Pharmacovigilance
EU	European Union
FDA	Food and Drug Administration
FU	Follow-up
GCP	Good Clinical Practice
GMA	Global Medical Affairs
GPP	Good Pharmacoepidemiology Practice
GPP	Good Publication Practice
GSL	Global Safety Lead
GVP	Good Pharmacovigilance Practice
ICD	International Classification of Diseases
ICH	International Conference of Harmonization
IEC	Independent Ethics Committee
IRB	Institutional Review Board

LHRH	luteinizing hormone releasing hormone
MAH	Marketing Authorization Holder
MedDRA	Medical Dictionary for Regulatory Activities
N/A	Not Applicable
OS	Overall Survival
PASS	Post-Authorization Safety Study
PBRER	Periodic benefit-risk evaluation report
PSUR	Periodic Safety Update Report
QPPV	Qualified Person Responsible For Pharmacovigilance
SAE	Serious Adverse Event
SSE	Symptomatic skeletal events

#### 4 Abstract

Acronym / Title	A Drug Utilization Study of Xofigo use in Sweden
Protocol version identifier	V 2.0
Date of last version of protocol	10-Oct-2014
IMPACT study number	17399
Study type	 non-PASS  PASS      Joint PASS:  YES  NO
Author	[name], Department of Clinical Science, Intervention and Technology, Karolinska Institutet
Rationale and background	
 
▪ Prostate cancer is the second most common cancer and the sixth leading cause of cancer mortality among men worldwide. A large number of men has disseminated disease at diagnosis or has a relapse after treatment with curative intent. Bone metastases and their clinical sequelae are among the most frequent and debilitating complications in patients with castration resistant prostate cancer (CRPC). Xofigo, a well-tolerated alpha-emitter with a half-life of 11.4 days, is a calcium mimetic that naturally self-targets to areas of increased bone turnover in bone metastases. It emits high-energy alpha particles of short range (less than 100 µm) that produce a potent and highly localized cytotoxic effect in the target areas. Xofigo was approved in the European Union on November 13, 2013 for the following indication: Xofigo is indicated for the treatment of adults with castration-resistant prostate cancer, symptomatic bone metastases and no known visceral metastases. Xofigo is contraindicated in women who are or may become pregnant. Xofigo can cause fetal harm when administered to a pregnant woman. Xofigo has not been tested on children. The purpose of this study is to evaluate use of Xofigo including potential off-label use in the post marketing setting.
 

Research question and objectives
	
The objective of this study is to evaluate the extent of potential off-label use of Xofigo in Sweden.
 
This study will include all patients for whom a medical decision has been made to treat with Xofigo. In particular, this study is designed to evaluate the use of Xofigo in
 
 
• Men with mCRPC
 
• women.
 
• children.
 
• Patients with bone metastasis but having a diagnosis of other cancer than CRPC.
 
• Patients with repeated courses of treatment or in excess of those recommended in the label.
 


Study design
	
This is a single arm descriptive observational drug utilization study of patients treated with Xofigo in Sweden.

Population
	
The study population are the persons receiving treatment of Xofigo at nuclear medicine centers across Sweden during a two year period. It will consist of patients for whom a medical decision has been made to treat with Xofigo. . This study will be based on data extracted from two pre-established secondary data sources: 15 Nuclear medicine centers across Sweden and the Swedish national cancer registry.

Variables
	
 
• Gender
 
• Age
 
• Cancer diagnosis/Indication for treatment
 
• Dosage level (kBq/kg), number of doses
 

Data sources
	
Two data sources will be used for the conduct of this study: 15 Nuclear medicine centers in Sweden and the Swedish National Cancer Registry
 
The investigator will manually record the Personal Identification Numbers (PINs) for all patients treated with Xofigo at the Nuclear Medicine Centers in Sweden. The PIN is an unique identification number for all inhabitants in Sweden including information on gender and birth year. Through a record-linkage between the Nuclear Medicine Centers and the National Swedish Cancer Registry based on the individuals' PINs, information on individuals' cancer diagnosis will be confirmed. Information on

	indication for treatment, dosage level (kBq/kg) and number of doses will be obtained from the Nuclear medicine centers.
Study size	All patients receiving treatment of Xofigo at participating nuclear medicine centers in Sweden during the two year period will be included in this study. It is estimated that about 200 patients will be treated with Xofigo during this period of time.
Data analysis	This is a single arm descriptive observational drug utilization study based on secondary data collection. This study is not aimed to confirm or reject pre-defined hypotheses. Statistical analyses will be descriptive in nature. All variables will be analyzed descriptively with appropriate statistical methods.
Milestones	Start of data collection: 15 November 2014 End of data collection: 30 June 2016 Final report of study results: 01 December 2017.

## 5 Amendments

None.

## 6 Milestones

Table 1 presents planned milestones for the project. These milestones are based on a timely review and approval of the project. Administrative changes to milestones due to delays in study preparation and enrolment do not require amendments to the protocol. The final report will be provided 17 months after study end since there is a lag time in reporting to the Swedish cancer registry.

**Table 1: Milestones**

Milestone	Planned date
Start of data collection	15 November 2014
End of data collection	30 June 2016
Registration in the EU PAS register	01 March 2014
Update in PSUR/ PBRER	Status will be provided in corresponding with PSUR/ PBRER submission schedule

Final report of study results

01 December 2017

## 7 Introduction: Background and Rationale

Prostate cancer is the second most common cancer and the sixth leading cause of cancer mortality among men worldwide. A majority of cancers (approx. 70 %) are curable or do only need surveillance. Even so a large number of men has disseminated disease at diagnosis or has a relapse after treatment with curative intent.

Prostate cancer spreads predominantly to the skeleton and to local lymph nodes. Treatment with luteinizing hormone releasing hormone (LHRH) analogue is the cornerstone of treatment for advanced prostate cancer. LHRH analogues lowers the testosterone level in the body and most tumours thrive on testosterone. The effect of lowering testosterone eventually weans off and the tumour starts growing again. This is called castration-resistant prostate cancer (CRPC).

In the last few years, several new treatments for patients with CRPC has evolved. Bone metastases and their clinical sequelae are among the most frequent and debilitating complications in patients with CRPC. Bone metastases are characterized by increased osteoclast activity and are associated with significant skeletal morbidity (ie, skeletal-related events(SREs), including fractures, radiation to bone, spinal cord compression, and surgery to bone). The underlying pathophysiology of bone metastases is an increased pathological rate of bone remodeling, including increased osteoclast activity. Several drugs have been approved to prevent pain and SREs in patients with CRPC, but none of these drugs improves survival.

In the phase III trial Alpharadin in Symtomatic Prostate Cancer Patients (ALSYMPCA), 921 patients with CRPC and bone metastases were enrolled and randomized between Xofigo and placebo treatment. Xofigo, a well-tolerated alpha-emitter with a half-life of 11.4 days, is a calcium mimetic that naturally self-targets to areas of increased bone turnover in bone metastases. It emits high-energy alpha particles of short range (less than 100 um) that produce a potent and highly localized cytotoxic effect in the target areas. The trial's primary endpoint was overall survival. Secondary endpoints included time to first symptomatic skeletal events (SSE) and quality of life measures. The term SSE was used because it more precisely describes the endpoint and discriminates between an endpoint composed of only symptomatically driven components and that including asymptomatic events.

Xofigo was approved in the European Union on November 13, 2013 for the following indication: Xofigo is indicated for the treatment of adults with castration-resistant prostate cancer, symptomatic bone metastases and no known visceral metastases. Xofigo is contraindicated in women who are or may become pregnant. Xofigo can cause fetal harm when administered to a pregnant woman. Xofigo has not been tested on children. The licensed dosage of Xofigo is 50kBq (1.35 microcurie) per kg body weight given at 4 weeks interval for six injections

## 8 Research questions and objectives

This study will include patients for whom a medical decision has been made to treat with Xofigo.

The primary objectives in this study are:

- To estimate the use of Xofigo for men with mCRPC
- To estimate the use of Xofigo in women.
- To estimate the use of Xofigo in children.
- To estimate the use of Xofigo in patients with bone metastasis but having a diagnosis of other cancer than castration resistant prostate cancer.
- To estimate the use of Xofigo in dosage level (kBq/kg) and number of doses outside recommendations.

### 8.1 Secondary objective(s)

Not applicable.

## 9 Research methods

### 9.1 Study design

This is a single-arm descriptive observational drug utilization study based on secondary data collection of patients treated with Xofigo in Sweden.

This study will include patients receiving treatment of Xofigo at certified nuclear medicine centers across Sweden during a two year period. It will consist of mCRPC patients and potentially some other patient groups in whom Xofigo may be used off-label including women, children, cancer patients having bone metastasis with a diagnosis other than CRPC, and patients with repeated courses of treatment or in excess of those recommended in the label. This study will be based on data extracted from two pre-established data sources: 15 nuclear medicine centers across Sweden and the Swedish National Cancer Registry.

The Personal Identification Numbers (PINs) for all patients treated with Xofigo at the 15 Nuclear Medicine Centers in Sweden will be extracted and recorded manually by the investigator. The PIN is a unique identification number for all inhabitants in Sweden including information on gender and birth year. Information on treatment indication, dosage level (kBq/kg) and number of doses will be obtained from the nuclear medicine centers. Information on if the patient is included in a clinical trial will also be obtained.

Through a record-linkage between the information provided from the Nuclear Medicine Centers and the Swedish National Cancer Registry based on the individuals' PINs, the cancer diagnosis will be confirmed.

### 9.1.1 Primary endpoint(s)

The primary endpoints are:

- The use of Xofigo in mCRPC
- The use of Xofigo in women.
- The use of Xofigo in children.
- The use of Xofigo in patients with bone metastasis but having a diagnosis of other cancer than mCRPC.
- The use of Xofigo in dosage level (kBq/kg) and number of doses outside recommendations.

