### 9.2.1 Inclusion criterion/criteria

Patients receiving Xofigo with data recorded at nuclear medicine centers in Sweden between 01 July 2014 and 30 June 2016 will be included in the study.

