## **9.5 Study Size**

The study size is depending on the market penetration of the product. It's expected that approximately 200 CRPC patients will receive Xofigo in Sweden in a two year period. The study is population based and should cover all patients who will receive Xofigo from all nuclear centers that are commercially licensed in Sweden (15 nuclear centers so far). Under the circumstances that the number of study sites or subjects are limited, the current study can be considered for an extension of another year (conditioning on that the market penetration is favorable). If additional nuclear centers become commercially licensed at a later time, they can be considered to be added to this study when it's necessary. The estimated sample size will be updated and communicated to the Agency in relation to PSUR/PBRER reporting schedule. Alternatively, a similar study in another European country is under evaluation. Whether such a study is feasible would depend on results from the feasibility assessment.

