## 9.7 Data analysis

### 9.7.1 Statistical considerations

Statistical analyses will be of descriptive nature. The study is not aimed to confirm or reject pre-defined hypotheses.

All variables will be analyzed descriptively with appropriate statistical methods: categorical variables by frequency tables (absolute and relative frequencies) and continuous variables by sample statistics (i.e. mean, standard deviation, minimum, median, quartiles and maximum). Patients receiving at least one dose of Xofigo will be included in the analysis. Whenever possible, Data will be stratified by subgroups (e.g. age, gender).

Sample size and disposition information by analysis time point will be displayed in a frequency table.

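### The dose-related primary endpoint is stated in two ways that count different patients: excess or repeated use in sections 4 and 9.1, any departure from recommendations in sections 8 and 9.1.1

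*Protocol*

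**What the plan says.** Four places in the protocol describe the dose-related question.

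- Section 4 (Abstract, objectives): "Patients with repeated courses of treatment or in excess of those recommended in the label".
- Section 9.1 (Study design): "patients with repeated courses of treatment or in excess of those recommended in the label".
- Section 8 (primary objectives): "To estimate the use of Xofigo in dosage level (kBq/kg) and number of doses outside recommendations".
- Section 9.1.1 (primary endpoints): "The use of Xofigo in dosage level (kBq/kg) and number of doses outside recommendations".

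The only reference regimen is in section 7: "The licensed dosage of Xofigo is 50kBq (1.35 microcurie) per kg body weight given at 4 weeks interval for six injections". No section says whether receiving fewer than six injections departs from the recommendation, or how a course that is unfinished at the end of the study period is classified.

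On who is analysed, section 9.7.1 says "Patients receiving at least one dose of Xofigo will be included in the analysis". Section 9.2.1 includes patients with data recorded "between 01 July 2014 and 30 June 2016 will be included in the study". Table 1 puts the end of data collection on the same closing date. Sections 9.3, 9.3.1 and 9.3.6 list dosage level and number of doses as the treatment variables, but neither injection dates nor course status.

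**The concern.** The first pair of statements points one way: more than the label, or a repeated course. The second pair has no direction and leaves repeated courses out. An analysis plan cannot follow both. If the choice is made once the dose counts are visible, the reported proportion depends on that choice.

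This matters because the abstract sets the aim as the extent of potential off-label use, and section 9.1.3 says the study answers a Health Authority request. A proportion made up mainly of shortened or unfinished courses tells the authority something quite different from one made up of patients treated beyond the label. The reader of the report would need to know which it is.

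**Working it through.** **No stated figure to reproduce.** The protocol attaches no number to this endpoint. The 200 in section 9.5 ("approximately 200 CRPC patients will receive Xofigo in Sweden in a two year period") is an uptake estimate with no precision target behind it.

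**Step 1: compare the definitions.**

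| | Sections 4 and 9.1 | Sections 8 and 9.1.1 |
|---|---|---|
| Direction | above the label | none given |
| Repeated courses | named | not named |
| kBq/kg | not named | named |

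Neither definition contains the other. A patient with one course of four injections is not in the first group but, read literally, is in the second. A patient with two short courses totalling exactly six injections is in the first group but, on number of doses, not in the second.

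**Step 2: courses cut off by the calendar.** Six injections at 4-week intervals span 5 × 28 = 140 days. The inclusion window, 1 July 2014 to 30 June 2016, is 731 days. Assume that start dates are uniform over the window and that no dose after 30 June 2016 is counted. The share of starters who cannot reach six injections, even if nobody stops early, is then 140/731 = 0.192, or 200 × 0.192 ≈ 38 patients.

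**Step 3: how far a single proportion could mix the two kinds of use.** Let *s* be the share of patients with fewer than six injections because they stopped early, and *e* the share in excess. Neither is in the protocol; both are assumptions. With N = 200:

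- directed count = 200 × *e*
- undirected count = 200 × (*s* + *e*)
- excess share of the undirected group = *e* / (*s* + *e*)

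Each cell gives the excess count over the undirected count, with the share:

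| *s* | *e* = 1% | *e* = 2% | *e* = 5% | *e* = 10% |
|---|---|---|---|---|
| 5% | 2/12 = 17% | 4/14 = 29% | 10/20 = 50% | 20/30 = 67% |
| 10% | 2/22 = 9% | 4/24 = 17% | 10/30 = 33% | 20/40 = 50% |
| 20% | 2/42 = 5% | 4/44 = 9% | 10/50 = 20% | 20/60 = 33% |
| 40% | 2/82 = 2% | 4/84 = 5% | 10/90 = 11% | 20/100 = 20% |

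The range is about 2% to 67%. The truncation in step 2 is a separate mechanism and is not included in this table.

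**The case against.** The sections that govern the analysis, 8 and 9.1.1, agree with each other. The lists in sections 4 and 9.1 are introduced as examples of groups of interest, so a broader endpoint need not contradict them. The number of doses is recorded for each patient and will be summarised descriptively. A frequency table would show everyone above six, no hypothesis is tested, and no section prescribes one pooled proportion. Row categories are normally left to the analysis plan.

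Much of this stands, and it rules out stronger readings that a reader might infer:

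- *That every patient who stops early is counted as outside the recommendation.* This is one literal reading. The protocol never defines the term and does not say that early stopping departs from the label.
- *That early stopping swamps excess use.* This depends on assumed rates. At 5% early stopping and 10% excess use, two thirds of the group is excess use.
- *That excess use would be lost.* Counts above six remain recoverable from a frequency table of doses. The harm is an ambiguous headline proportion.
- *That 19% of courses will be truncated.* Section 9.2.1 dates the inclusion of patients and states no rule for counting doses. The figure needs both assumptions in step 2.
- *That below-label use should be kept out of the off-label total.* That is a labelling question which the protocol does not settle.

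The objection does not remove the inconsistency. As step 1 shows, the endpoint is not simply a broader version of the lists, because repeated courses drop out of it. A dose frequency table does not repair this either. Without dates or course status, a count below six cannot be divided into ended and still-open courses, and a repeated course totalling six or fewer cannot be recognised.

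**Conclusion.** The concern holds as an inconsistency in the definition of a primary endpoint. This is certain from the text and needs no assumption. It follows that one undirected proportion can combine shortened courses, unfinished courses and excess use.

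How much it would do so cannot be derived from the protocol. The 2% to 67% range shows only that the answer could go either way, and it rests wholly on the assumed rates. The truncation figure uses the protocol's own dates and interval, but also needs uniform starts and no doses counted after 30 June 2016. The later final-report date does not establish otherwise: sections 6 and 9.9 explain it by the lag in cancer registry reporting and do not mention dose follow-up.

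**What to change.** Reconcile sections 4, 8, 9.1 and 9.1.1 into one definition before data lock, and say explicitly whether repeated courses belong to it. Report these rows separately:

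1. above the label number of injections;
2. repeated course;
3. equal to the label number;
4. below it, course ended;
5. course still open at cut-off.

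Split kBq/kg into above and below in the same way. State whether doses after 30 June 2016 are counted, and state in advance which rows enter the off-label total. Which rows those are is for the sponsor to settle.

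The cost is a wording change, a table layout and one small addition to data collection: injection dates or course status must go on the CRF, because the listed variables cannot separate rows 4 and 5 or identify every repeated course. The change alters no dose or treatment rule.

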### 9.1.2 Secondary endpoint(s)

Not applicable.

### 9.1.3 Strengths of study design

The proposed study will capture information on Xofigo utilization and potential off label use among patients receiving Xofigo in Sweden during a 2 year study period. The proposed data sources will be extracted from two pre-existing data systems, the certified nuclear medicine centers across Sweden and the Swedish National Cancer registry. This study employs a simple approach to obtain relevant data through record linkage of two secondary data sources to address the request from Health Authority. This design eliminates the potential recall bias since all data collection will be done through registers.

## 9.2 Setting

The study population are the persons receiveing treatment with Xofigo at nuclear medicine centers in Sweden during a two year period.

### 9.2.1 Inclusion criterion/criteria

Patients receiving Xofigo with data recorded at nuclear medicine centers in Sweden between 01 July 2014 and 30 June 2016 will be included in the study.

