1.1 Does the protocol specify timelines for				
1.1.1 Start of data collection 	x			
1.1.2 End of data collection 	x			
1.1.3 Study progress report(s)			x	
1.1.4 Interim progress report(s)			x	
1.1.5 Registration in the EU PAS register	x			
1.1.6 Final report of study results.	x			

Comments:

Section 2: Research question	Yes	No	N/A	Page Number(s)
2.1 Does the formulation of the research question and objectives clearly explain:				
2.1.1 Why the study is conducted? (e.g. to address an important public health concern, a risk identified in the risk management plan, an emerging safety issue)	x			
2.1.2 The objective(s) of the study?	x			
2.1.3 The target population? (i.e. population or subgroup to whom the study results are intended to be generalised)	x			

 Date from which information on the first study is first recorded in the study dataset or, in the case of secondary use of data, the date from which data extraction starts.

 Date from which the analytical dataset is completely available.

Section 2: Research question	Yes	No	N/A	Page Number(s)
2.1.4 Which formal hypothesis (-es) is (are) to be tested?			x	
2.1.5 If applicable, that there is no a priori hypothesis?	x			

Comments:

Section 3: Study design	Yes	No	N/A	Page Number(s)
3.1 Is the study design described? (e.g. cohort, case-control, randomised controlled trial, new or alternative design)	x			
3.2 Does the protocol specify the primary and secondary (if applicable) endpoint(s) to be investigated?	x			

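### Inclusion and data collection end on the same day, so late starters' dose counts are cut short for the number-of-doses endpoint

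*Protocol*

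**What the plan says.** - **Inclusion.** Section 9.2.1 takes in patients with "data recorded at nuclear medicine centers in Sweden between 01 July 2014 and 30 June 2016 will be included in the study". It does not require the first injection to fall inside the window.
- **End of collection.** The Abstract gives "End of data collection: 30 June 2016", and Table 1 in section 6 repeats the date. Collection starts on 15 November 2014.
- **Course.** Section 7 describes the licensed dosage as 50 kBq "per kg body weight given at 4 weeks interval for six injections".
- **Endpoint.** Section 9.1.1 lists as its fifth primary endpoint "The use of Xofigo in dosage level (kBq/kg) and number of doses outside recommendations". Section 9.1 names among the off-label groups of interest "patients with repeated courses of treatment or in excess of those recommended in the label".
- **Exposure data.** Sections 9.3, 9.3.1 and 9.3.6 list dosage level and number of doses. Injection dates are not listed.
- **Time to report.** Sections 6 and 9.9 attribute the 17 months between study end and the final report to cancer-registry lag.
- **Checklist.** Footnote 2 in Annex 2 explains the end-of-data-collection milestone as "Date from which the analytical dataset is completely available".

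**The concern.** A patient can enter on any day up to 30 June 2016, and recording stops that day. Someone first treated in spring 2016 is analysed (section 9.7.1 asks only for one dose), but the recorded count reflects the calendar and not the course given. Without injection dates, a course cut off by the calendar cannot later be told from one that ended early, and no analysis plan can recover the difference.

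Two errors follow. A seventh injection or a repeat course after the cut-off is never seen, so excess use is undercounted. If falling outside recommendations also covers fewer than six doses, open courses are miscounted as short ones. The study exists to measure off-label use, so the first error bears directly on its purpose.

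A similar gap exists at the start. The product was approved on 13 November 2013, so some patients may have been mid-course on 1 July 2014, and the protocol does not say whether their earlier injections count.

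**Working it through.** **Inputs.** Window 1 July 2014 to 30 June 2016 (9.2.1); end of collection 30 June 2016 (Abstract, Table 1); six injections four weeks apart (section 7); about 200 patients (9.5); approval 13 November 2013 (section 7); report 1 December 2017 (Table 1).

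**The plan's own timeline.** The window is 365 + 366 = 731 days, which agrees with the stated two years. From 30 June 2016 to 1 December 2017 is 17 months, as stated. The figure of 200 is a market estimate without inputs and cannot be re-derived.

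**Observation time needed, on schedule.**
- First to sixth injection: 5 × 28 = 140 days.
- First to seventh at the same interval: 6 × 28 = 168 days.
- Observation after the last inclusion: 0 days.

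**Latest start that allows each to be seen.**
- Sixth: 30 June 2016 minus 140 days = 11 February 2016.
- Seventh: 30 June 2016 minus 168 days = 14 January 2016.

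**Share with too little observation time, assuming uniform starts inside the window.**
- Sixth: 140/731 = 19.2%; 0.192 × 200 ≈ 38 patients.
- Seventh: 168/731 = 23.0%; 0.230 × 200 ≈ 46 patients.

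**Share that actually loses a dose.** A patient who would receive m doses loses at least one if the start falls in the last (m − 1) × 28 days. This is linear in m, so the mean can be used. The protocol gives no mean, so these are assumptions:

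| Assumed mean doses | Calculation | Share losing a dose |
|---|---|---|
| 5 | 112/731 | 15.3% |
| 4 | 84/731 | 11.5% |
| 3 | 56/731 | 7.7% |

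**Start of the window.** On schedule, patients first treated between 11 February and 30 June 2014 (140 days) would still be in a course on 1 July 2014. If use was already steady then, they join the denominator: 731 + 140 = 871, and 140/871 = 16.1% (about 32 of 200) are affected at each end. The left-hand share applies only if earlier injections are not captured, which the protocol leaves open.

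**After the fix.** A cut-off at 30 June 2016 + 140 days = 17 November 2016 lets every included patient be observed to a scheduled sixth injection. At + 168 days = 15 December 2016 the same holds for a seventh. Both dates precede the report.

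**The case against.** **The milestone may only be loosely labelled.** Sections 6 and 9.9 treat 30 June 2016 as study end and place the registry wait after it, so registry linkage must come later whatever the milestone is called. The checklist footnote therefore shows an ill-fitting milestone; it does not itself prove that doses are cut off. This stands. But no passage plans dose recording after that date, and the 17 months are set aside for the registry alone. The one-year extension in section 9.5 is conditional and would move the closing date without adding follow-up after the last inclusion.

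**A reader might infer that injections before 1 July 2014 are ignored.** The protocol does not say so. Section 9.2.1 defines which patients enter, collection begins after the window opens and so is partly retrospective, and centre records may hold earlier injections. The gap is silence on the handling, not a rule to discard.

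**A reader might take one in five as a minimum for patients losing doses.** It is the share with a short observation window under uniform starts. Early stopping lowers the number who lose a dose. Rising uptake would increase the share of late starters, but the protocol gives no uptake curve. Nor does it give an interval before a repeat course, so no larger figure is supported.

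**An open course counts as off-label only on one reading.** Section 9.1 speaks of repeated or excess treatment. On that reading a truncated course is not misclassified as off-label, and only the undercount of excess and repeat use remains. This also stands.

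**The analysis plan may cover open courses.** Tabulation can be left to it. The recording cut-off and the collection of injection dates cannot, because they determine what data exist.

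**Conclusion.** The point holds as a defect in the data-collection window. With uniform starts, about 19% of in-window starters lack the time for a scheduled sixth injection and about 23% for a seventh. About 8% to 15% would actually lose a dose at an assumed mean of 3 to 5. These figures rest on even uptake and four-week intervals. Excess and repeat use is biased downwards; whether open courses are also miscounted depends on how the endpoint is read. Undercounting of patients who enter mid-course in July 2014 is an unaddressed risk whose size the documents do not fix.

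It should be fixed but is not critical. The study is descriptive, and use in mCRPC, in women, in children and in other cancers is untouched, as is dose level in kBq/kg. Only the dose-count part of one of five primary endpoints is affected.

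**What to change.** 1. Keep 1 July 2014 to 30 June 2016 as the inclusion window, and state that it selects patients and does not limit the injections counted.
2. Add the date of every injection to the variables in sections 9.3.1 and 9.3.6 and to the CRF.
3. For each included patient, extract all injections from the first ever, including any before 1 July 2014, to a fixed cut-off at least 168 days after 30 June 2016, that is 15 December 2016 or later. Choose a later date if repeat courses after a gap are to be captured.
4. Move the end-of-data-collection milestone in the Abstract and Table 1 to match.
5. Report courses still open at the cut-off in a separate row.

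The cost is protocol wording and one later extraction at the same centres, with the paper CRF, double entry and checks that sections 9.6 and 9.8 require. A December 2016 cut-off leaves almost a year before the 1 December 2017 report, and the work can run alongside the registry wait.
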